6.9 UNFAVORABLE BIOPSY FINDINGS REQUIRING REINSTITUTION OF IMMUNOSUPPRESSION

The protocol biopsy performed 52 weeks following discontinuation of all immunosuppression will be assessed by **Table 1** by central pathology. The presence of any or all of the histological findings described in **Table 1** on a follow-up biopsy after initiation of immunosuppression withdrawal suggests that participants are unlikely to benefit from minimal or no immunosuppression⁴. Participants who demonstrate any of the histological findings in **Table 1** will not be required to restart immunosuppression by this protocol; clinical management will be determined by the local pathology read and discussion with the participant (see section 6.10.2). Such participants will still be considered to have failed immunosuppression withdrawal.

6.10 LIVER BIOPSY

6.10.1 Types of Biopsies

- Protocol Biopsies

- Participants will undergo liver biopsies at times specified in the schedule of events (see Appendices 1 and 2). These biopsies will be used to monitor liver function, to screen for subclinical rejection, and for mechanistic analyses.
- For-cause Biopsies
 - For-cause biopsies (FCB) will be obtained to confirm suspected rejection following unexplained allograft dysfunction (see Section 6.6 for definition) and all mechanistic assessments listed in Appendix 5 should be performed.

6.10.2 Use and Interpretation of Liver Biopsies

All liver biopsies will be analyzed per the Banff global assessment criteria¹⁻³ by the central pathology laboratory. All protocol and for-cause biopsies will be analyzed by the local pathology laboratory. The guidelines for the use of these pathology reports are outlined below:

6.10.2.1 Protocol Biopsies

All protocol biopsies will be read by both the central and local pathologist. The central pathology read will be used for the purposes of analysis and determination of eligibility for immunosuppression withdrawal, and for assessment of the primary endpoint. The local pathology read will be used for the purposes of clinical management. The central pathology read will be available to the investigators for consideration at their discretion.

6.10.2.2 For-Cause Biopsies

The local pathology read will be used for clinical management for all for-cause biopsies. The central pathology read will be used for the purposes of analysis in conjunction with any clinical treatment to determine study outcomes such as reported rates of rejection.

Central pathology reads will also be collected for for-cause biopsies, but not used for treatment or determining rejection due to the time lag in reporting.

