6.7.1 Acute Rejection

Acute allograft rejection will be defined in accordance with Banff global assessment criteria^{1-3,65}.

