7.3. Secondary Endpoints

All secondary endpoints will be analyzed as described in Table 7-2. Mock displays for these results are outlined in the Appendix.

Table 7-2 Table of Endpoints and Analysis Methods

Endpoint	Method	Population
Primary		
The proportion of participants who achieve operational tolerance 52 weeks after completion of immunosuppression withdrawal.	Proportion of participants who achieve operational tolerance 52 weeks after completion of immunosuppression withdrawal with a corresponding two-sided 95% exact binomial confidence interval.	ITT, PP
Secondary		
Safety		
The proportion of participants who develop DSA or de novo anti-HLA antibodies after initiation of immunosuppression withdrawal.	Proportion of participants who develop DSA or de novo anti-HLA antibodies after initiation of immunosuppression withdrawal with a corresponding two-sided 95% exact binomial confidence interval.	ITT, PP
The incidence, severity, and timing of acute rejection, steroid resistant rejection, and chronic rejection.	
Acute Rejection: Incidence will be measured as the proportion of participants who have acute rejection (per Banff criteria) with a corresponding two-sided 95% exact binomial confidence interval.
 
Severity will be measured according to the Banff grade. Acute rejection can be expressed as mild, moderate or severe. This will be summarized descriptively with counts and percentages.
	ITT, PP
	
Steroid Resistant Rejection: Incidence will be measured as the proportion of participants who have steroid resistant rejection (rejection requiring antibody treatment) with a corresponding two-sided 95% exact binomial confidence interval.
 
All steroid resistant rejections are considered severe in nature and nothing further will be summarized.
	
	
Chronic Rejection: Incidence will be measured as the proportion of participants who have chronic rejection (per Banff criteria) with a corresponding two-sided 95% exact binomial confidence interval.
	

	
Severity will be measured according to the Banff grade. Chronic rejection can be expressed as early or late. This will be summarized descriptively with counts and percentages.
 
For all rejection types, timing will be expressed as the time from the initiation of immunosuppression withdrawal to the time of the first biopsy showing acute rejection and will be summarized descriptively.
 
All data presented will use the central read.

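### The protocol contradicts itself on whether central reads of for-cause biopsies determine rejection, and the SAP's rejection incidence leaves out treated or presumed episodes that no central read confirms

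*Protocol*

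**What the plan says.** **Protocol 6.10.2.2.** The first paragraph gives clinical management of for-cause biopsies to the local read and analysis to the central read, the latter "in conjunction with any clinical treatment to determine study outcomes such as reported rates of rejection". The second paragraph says central reads are also collected, "but not used for treatment or determining rejection due to the time lag in reporting".

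**Protocol 6.7.** For acute rejection, 6.7.1 says: "Acute allograft rejection will be defined in accordance with Banff global assessment criteria". Section 6.7.2 does the same for chronic rejection. Neither names the read. Section 6.7.3 defines presumed rejection separately, as allograft dysfunction treated with more immunosuppression without a confirming biopsy. A biopsy is due within a week unless contraindicated. If it is negative, the participant may continue withdrawal; if it is positive or cannot be done, the participant has failed withdrawal. Section 3.1.3.5 agrees on the negative case.

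**Consequences for the participant.** Protocol 6.8 reinstates immunosuppression for biopsy-confirmed or presumed rejection. Protocol 9.2.1 makes failure to complete withdrawal, or resumption before 52 weeks, a primary endpoint failure; SAP 7.2.1 is to the same effect.

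**SAP Table 7-2, rejection row.** Acute and chronic rejection are counted by Banff criteria. Timing for every rejection type runs "to the time of the first biopsy showing acute rejection". The row closes: "All data presented will use the central read". Steroid-resistant rejection is the one type defined by a treatment (antibody). Neither Table 7-2 nor the mock safety table in the SAP Appendix has a line for presumed rejection.

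**The concern.** There are two faults. The protocol gives two incompatible statements about the same read in adjacent paragraphs. The SAP then settles on the central read and drops the treatment component that the first paragraph attaches to it.

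The result is two working definitions of rejection in one report. Management, resumption of immunosuppression and failure of withdrawal follow the local read or clinical suspicion. Incidence and timing follow the central read. A participant can be non-tolerant because of a treated rejection and still not appear in rejection incidence. Protocol 1.3.1 and 1.4.1.1 name rejection as the primary risk of withdrawal, so a reader of the safety table will expect these participants to be visible there.

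The same gap appears in three other places. Primary endpoint criterion (a), no evidence of rejection since enrollment, names no read, although criteria (b) and (c) do. Stopping guideline 2 in Protocol 3.5 is monitored continuously and names no read. SAP 8.5.3.2 summarises treatment per rejection episode without saying which read makes an episode.

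**Working it through.** **Step 1: episode types side by side (before 52 weeks).**

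| Episode | Withdrawal status | SAP acute rejection incidence |
|---|---|---|
| Local positive, treated, central positive | Failure | Counted |
| Local positive, treated, central negative | Failure (management follows the local read; immunosuppression restarted) | Not counted |
| Presumed, biopsy not possible | Failure (3.1.3.5, 6.7.3) | Not counted; no biopsy date for timing |
| Presumed, later biopsy negative | May continue withdrawal (3.1.3.5, 6.7.3) | Not counted, consistent with the protocol |
| Local negative, central positive | Depends on which read criterion (a) uses | Counted |

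Rows two and three are the omission. Row four should stay out. Row five runs in the opposite direction.

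**Step 2: reproduce the plan's interval method.** The SAP uses exact binomial intervals: lower limit = Beta quantile at 0.025 with parameters (x, n−x+1); upper limit = Beta quantile at 0.975 with (x+1, n−x). For 24/60 this gives 27.56% to 53.46%, and for 36/60 it gives 46.54% to 72.44%. Both agree with Protocol 9.3 (27.6 to 53.5; 46.5 to 72.4). No stated figure is in dispute.

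**Step 3: size per participant.** N = 60 (Protocol 9.3), so 1/60 = 1.7 percentage points for each participant not counted.

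**Step 4: illustration.** Protocol 1.4.1.1 expects 50% to have a rejection episode, that is 30/60 = 50.0% (95% CI 36.8 to 63.2). Let these 30 be the participants treated for locally diagnosed or presumed rejection. Let k be the number with no central confirmation and g the number positive on the central read only. The central-only count is 30 − k + g. The documents give neither k nor g; k from 0 to 9 is an assumed range.

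| k | g | Central-only count | Rate (95% CI) |
|---|---|---|---|
| 0 | 0 | 30 | 50.0% (36.8 to 63.2) |
| 1 | 0 | 29 | 48.3% (35.2 to 61.6) |
| 3 | 0 | 27 | 45.0% (32.1 to 58.4) |
| 6 | 0 | 24 | 40.0% (27.6 to 53.5) |
| 9 | 0 | 21 | 35.0% (23.1 to 48.4) |
| 3 | 3 | 30 | 50.0% |
| 3 | 6 | 33 | 55.0% |

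Protocol 1.3.1 cites an earlier withdrawal trial with 57/98 = 58%, which is about 35/60 = 58.3% (44.9 to 70.9). From that start, k = 3 gives 32/60 = 53.3% and k = 6 gives 29/60 = 48.3%, with g = 0.

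**Step 5: what is certain.** A count combining all sources is 30 + g. Its difference from the central-only count is (30 + g) − (30 − k + g) = k, which is never negative. The central-only rate may still lie above or below the rate for locally diagnosed and presumed episodes, depending on whether g exceeds k.

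**The case against.** The other side has several sound points.

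- The reason given in the second paragraph of 6.10.2.2, reporting lag, fits real-time diagnosis better than end-of-study analysis. On that reading the SAP follows the intended split of local for management and central for analysis. This is plausible, but the sentence lists treatment and determining rejection as separate items and does not limit itself to real time.
- Leaving cases without a biopsy out of a Banff incidence agrees with 6.7.1, and no Banff grade can be given without tissue. This stands, and it argues for a separate row over merging them into the Banff row.
- Such cases should be few. Section 6.7 requires biopsy confirmation unless contraindicated, and exclusions 9 and 12 remove candidates who could not safely have, or comply with, biopsies. This limits the size but gives no number.
- The episodes are not lost. They are recorded as adverse events regardless of grade (8.2.2, 8.4.4), reasons for discontinuing withdrawal are tabulated (SAP 5.1), and the resumption rule largely protects the primary endpoint. This stands too.

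A reader might go further and infer that the SAP understates the trial's main safety endpoint. The documents do not support that. Protocol 3.3.2 lists this endpoint second of six, unranked. Central reads can add rejections as well as remove them. A reader might also infer that the first paragraph of 6.10.2.2 calls for counting an episode that is either centrally positive or treated. It says only that the two are used in conjunction, which could equally require both; the central-only count would then be equal to or higher than the protocol's. A plain either-or rule would also count presumed cases with a later negative biopsy, whom the protocol allows to continue.

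**Conclusion.** The point holds as a conflict of wording plus an omission in the SAP. The two paragraphs of 6.10.2.2 cannot both stand as written. SAP Table 7-2 omits the treatment component and has no place for presumed rejection without a biopsy or for treated, centrally negative rejection. One secondary safety endpoint, covering the trial's primary risk, is affected directly.

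The size is 1.7 percentage points per uncounted participant at N = 60. The direction is certain, and downward, only for presumed cases without a biopsy. For disagreement between reads, neither the net sign nor the total can be derived from the documents. The illustrative rates rest on the protocol's 50% expectation and an assumed number of unconfirmed cases.

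**What to change.** 1. Reconcile the two paragraphs of Protocol 6.10.2.2, for example by stating that the second concerns real-time management only, if that is what was meant. Say how clinical treatment enters the analysis.
2. In SAP Table 7-2 and the mock safety table, keep centrally confirmed Banff rejection as its own row. Add one row for rejection diagnosed locally and treated but centrally negative, one for presumed rejection without a biopsy, and one combined count with each participant counted once. State the date used for timing where there is no biopsy.
3. Do not count presumed cases whose later biopsy was negative for rejection.
4. State which read defines the absence of rejection in primary endpoint criterion (a), an episode in SAP 8.5.3.2, and the events counted for stopping guideline 2.

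The cost is wording and a few table rows. Both reads (Protocol 6.10.2), all rejection episodes (8.4.4) and daily immunosuppression records (SAP 7.2.1) are already collected. The combined rate will equal the central-only rate or be somewhat less favourable.

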6.10.3 Liver biopsy assessments

All biopsies read by the central pathology core will be scored for 40 histopathological features. Biopsies will be assessed for adequacy, length, and the total number of portal tracts, with and without bile ducts. Necro-inflammatory activity, fibrosis, and architectural distortion will be graded according to the Ishak scale. AR- and CR-related activity will be graded and staged according to Banff criteria^{1,3,83}. Patterns of fibrosis not directly attributable to hepatitis, AR, or CR will be scored on a scale of minimal (barely detectable), mild, moderate, and severe (bridging). Architectural distortion will be assessed by variability of lobular size evidenced by measured portal-to-central distance. Changes potentially associated with chronic immunosuppression including 1) hepatic artery branch hyalinosis; and 2) nodular regenerative hyperplasia will also be assessed. Since consensus scales for these parameters do not exist, they will be scored according to a semi-quantitative scale.

7. MECHANISTIC ASSAYS

7.1 RATIONALE FOR IMMUNE STUDIES

A key objective of this investigation is discovery of a multiparameter biomarker composed of demographic, cellular or molecular markers that would prospectively identify liver transplant recipients who can withdrawal all immunosuppression successfully with little or no risk of experiencing allograft rejection. Many of these analyses will be exploratory in nature. The recent demonstration that the likelihood of immunosuppression withdrawal success depends on time post-transplant and age suggests that operational tolerance is a dynamic process that evolves with time. We hypothesize that identification of combinations of molecular and cellular biomarkers in conjunction with demographic information may accurately characterize the subset of operationally tolerant patients thereby allowing withdrawal of immunosuppression in those most likely to succeed. Specifically, in collaboration with the ITN mechanistic core and the following investigators [REDACTED]

[REDACTED] we may investigate the following areas:

1. Multi-parameter flow cytometry of peripheral blood lymphocyte subsets including markers of senescence/exhaustion.
2. Signature of miRNA in blood, PBMC, serum and/or graft biopsy specimens.
3. Histological characterization of graft specimens from tolerant and non-tolerant patients.
4. Transcription signature in blood and/or PBMC, graft biopsy, and/or urine pellet mRNA.
5. Serum and molecular markers of iron metabolism
6. HLA typing and alloantibody monitoring
7. Assessment of the extent of hepatopoeitic microchimerism using STR
8. Microbiome composition
9. Recipient cell reactivity to donor cell/material

7.2 MULTI-PARAMETER FLOW CYTOMETRY (MFC) AND TETRAMER ANALYSIS

We have hypothesized that the dynamic development of operational tolerance in liver recipients occurs at least in part through a process of immunosenescence and lymphocyte exhaustion. Specifically, that thymic atrophy-associated reduction in the production of new alloreactive clones in conjunction with the chronic exposure of recipient T cells to high levels of donor antigen expressed by the graft leads to a gradual attrition or functional exhaustion of donor reactivity. With this thesis in mind, MFC panels may be designed with the ITN flow cytometry core and [REDACTED] to detect recent thymic emigrants (e.g., CD103, CCR5), T cells with evidence of replicative senescence (e.g., identified by telomere shortening), and markers of lymphocyte exhaustion (e.g., CD57-, PD-1+). These studies may be

performed in parallel with investigation of general B and T cell subsets along with other reported flow based markers of tolerance in transplant patients, for example $\gamma\delta$ -T cells, NK T cells, Tregs and transitional and regulatory B cell subsets.

Flow cytometry may be performed on banked, frozen PBMC in batches at (an) appropriate timepoint(s). These experiments may be used to identify cell populations, cytokine production, and activation states. MFC data would be interpreted in conjunction with the other cellular, molecular, and immunologic assays that will be done in this trial as well as clinical data such as participant age, immunosuppression, rejection history, alloAb and DSA profiles, allograft histology, gene expression data, and longitudinal progress and outcome of immunosuppression withdrawal.

A central tenet to the argument that immunosenescence and lymphocyte exhaustion are responsible for development of operational tolerance in liver transplant recipients is that changes in the T cell repertoire or phenotype should be manifest in the donor specific subset of T cells. Inspection of donor specific T cell should provide greater sensitivity of analysis and will allow an internal control of non-donor specific T cells to account for global population changes due to age and pathogen exposure. For example, by using either donor type stimulation and/or specific tetramers we may be able to examine donor specific changes in T cells with focus on markers of exhaustion and replicative senescence. If tetramers are used, we anticipate availability for approximately 70% of the patients in the study based on common HLA types.

Table 5. Potential markers for discriminating exhausted vs. senescent cells via flow cytometry

Exhaustion	Senescence
+ PD-1	shortened telomere length
+ CTLA-4	↑ KLRG-1
+ TIM-3	↑ p38 MAP kinase
+ LAG-3	- CD28
+ BIM	+ CD57
+ BLIMP-1	↓ CD31
- CD62L	
- CCR7	
- IL-7R	
- IL-15R	
- CD28	

7.3 DISCOVERY OF A MIRNA SIGNATURE OF OPERATIONAL TOLERANCE

A novel aspect of our proposal is to explore micro RNA correlates with operational liver transplant tolerance in samples of blood serum and graft tissue.

miRNA's, which are small 20-25 nucleotide single stranded molecules, have recently gained prominence as master regulators of gene expression through translational repression and/or mRNA degradation⁴¹⁻⁴⁴. More than 700 miRNA's have been identified and their critical role in immune system development⁴⁵⁻⁵¹ the regulation of innate and adaptive immunity and may be key in T cell, B cell and Treg differentiation and function⁴⁴. That the miRNA might also be involved in the regulation of tolerance versus rejection seems almost certain but this remains an area with little data⁵². In a recently reported analysis by

Suthanthiran's team, miRNAs were differentially expressed in rejecting kidney biopsies compared with biopsies showing normal histology. miRNA were selected by hierarchical clustering for assessment in a biopsy validation set. Two of the miRNA (miR-142-5p and miR-155) accurately predicted rejection with 100% sensitivity and 95% specificity. A second study with similar objectives using slightly different methodology also identified a panel of miRNA associated with rejection however there was no overlap between miRNA found significant in the two studies^{41,52}.

Despite their discordance as to which miRNA correlated with rejection, these studies reveal the enormous potential for miRNA as a diagnostic tool in the transplant setting. An important and novel component of the proposed mechanistic studies is we may perform miRNA analysis of serum, blood and liver tissue to identify a miRNA signature of operational liver graft tolerance. Two approaches may be applied. First, a PCR-based approach may be used to evaluate known miRNAs, and second, next generation sequencing may be used to capture both known and currently unknown miRNAs that may be associated with operational liver tolerance. As far as we are aware, such an analysis has not yet been performed in prospectively weaned liver transplant recipients. This approach holds some theoretical advantages over a transcriptome microarray survey based on the more limited number of miRNAs as well as the practical advantage that miRNAs are stable in serum. The studies represent a new and potentially powerful addition to studies reported to date searching for a molecular signature of tolerance.

7.4 SERUM AND MOLECULAR MARKERS OF IRON METABOLISM AND OPERATIONAL TOLERANCE

An unexpected observation in the recent immunosuppression withdrawal studies of [name] was that tolerance was associated with serum and molecular markers associated with iron homeostasis⁸. By microarray analysis, the transcriptional profile of operationally tolerant recipients was dominated by genes involved in iron metabolism including HAMP, TFRC (the genes with the greatest fold change), FTHL12, FTHL8, EPHX1, A2M, CP, FTHL3, FTHL11, ABAT and SFXN4. In the serum, collected prospectively from participants successfully weaned from immunosuppression the levels of hepcidin, the master regulator of iron metabolism, and ferritin were elevated and there was greater iron deposition in graft hepatocytes. We may follow up on these findings using samples from this new participant cohort and measure serum and/or graft iron makers and use Q-PCR to analyze previously detected genes in iron metabolism pathways prior to withdrawal and at the 1 and 2 year time point post successful weaning or rejection.

7.5 HISTOLOGICAL ASSESSMENTS OF TOLERANCE MECHANISMS

Liver allograft biopsy remains the gold standard diagnostic modality for detection of allograft rejection. Whether careful histological assessment may also provide a reliable measure of tolerance has been recently examined by [name] et al in pediatric patients¹⁶ and is to be studied further in an NIH sponsored immunosuppression withdrawal trial in pediatric patients. [name] has generously shared their investigative plan using multiplex antigen labeling⁸⁴, to evaluate intragraft structural and phenotypic markers prior to immunosuppression withdrawal. The proposed staining panels are shown below (**Table 6**). Panels will be finalized at the time of experimentation to reflect the most current markers based on literature and state-of-the-art. A detailed focus on intragraft events is consistent with the notion that graft induced immune exhaustion is central to tolerogenic events.

We may test the hypothesis that the liver allograft itself plays a critical role in the development and maintenance of tolerance. To do so, we would rely on a histological analysis that parallels that in Dr.

[name]'s planned trial, and/or the literature and state-of-the-art at the time of assessment. This has the advantage of permitting comparison of the pediatric and adult withdrawal cohorts. The findings would be interpreted in conjunction with the other cellular, molecular, and immunologic assays that will be done in this trial.

Table 6. Potential Multiplex Staining Panels for Liver Biopsy Specimens

C4d/CD31	Determine the extent and intensity of C4d deposits on the hepatic microvasculature as a barometer of anti-donor reactivity; test the hypothesis that a total C4d score ≥ 6 is associated with failed IS withdrawal
CD3/ $\gamma\delta$ -1/ $\gamma\delta$ -2	Test the hypothesis that a portal tract ratio of $\gamma\delta$ -1/ $\gamma\delta$ -2 > 1.0 is associated with operational tolerance because the liver microenvironment is hostile to effector and memory T cell development and survival.
CK19/CD31/HLADR	Test the hypothesis that inappropriate expression of HLA-DR on the bile ducts is associated with failed IS withdrawal Monitor important rejection targets (CK19 biliary epithelium; and CD31-endothelium) for immune activation and rejection-related reactivity via up regulation of HLA-DR, which is not normally expressed.
CD3/CD45RO/CD45RA	Monitor the relative ratio of naïve to memory T cells; test the hypothesis that an increase in portal-based CD3+/CD45RO+ (memory) T cells is associated with failed IS withdrawal
CD4/Tbet/GATA-3/IL-17/FoxP3	Monitor the polarization of CD4+ lymphocytes within the allograft to determine whether an increase of putative regulatory T cells contributes to tolerance
IL10/TGF β /HLADR	Monitor expression of immunomodulatory cytokines by HLA-DR expressing cells in the liver such as Kupffer's cells and B cells.
CD56/PD-1/CD3	Determine the relative number/ratio of CD3+, CD56+, and PD-1+ lymphocytes and whether changes in NKT cells in the liver is associated with operational tolerance
CD5/CD19/CD27/IgG	Determine the ratio of naïve to memory B cells and B1:B2 intrahepatic B cells and whether memory B cells or B-regulatory cells that reside in the liver might contribute to allograft acceptance or rejection

